T deficiency is often treated with testosterone therapy of which various delivery methods are available³. Treatment is aimed at inducing and maintaining secondary sex characteristics and improving sexual function, sense of well-being, and bone mineral density⁴. Although testosterone was first synthesized in 1935, treatment options are continually evolving⁵.

One standard treatment for TD is intramuscular (IM) injections of exogenous T⁶. However, subcutaneous (SQ) injections may have some advantages compared to IM injections. SQ injections is more convenient and less challenging than IM for men who are candidates for self-injection. SQ also involves a smaller needle and may be less intimidating to patients. This trial will investigate how serum testosterone levels are affected by the route of T administration.

1.2. **Rationale and hypothesis**

The purpose of this study is to preliminarily determine if the route of delivery of testosterone therapy affects testosterone concentrations in men. Our hypothesis that SQ will provide comparable or acceptable T concentrations as IM, with regard to duration of action and peak or average concentrations.

2. Objectives

2.1. **Primary outcome and endpoint (endpoint bulleted below)**

The primary objective of this study is to determine how testosterone concentration in men differs based on administration route for T injections in men.

The Primary endpoints are total testosterone concentration and calculated free T concentration following injection, measured by Beckman assays and equipment.

2.2. **Secondary outcomes and endpoints (endpoints bulleted below)**

The Secondary endpoints are responses to Low Testosterone Questionnaire, International Prostate Symptom Scores, and levels of estradiol, LH, FSH, SHBG, and PSA following injection, measured by Beckman assays and equipment and hematocrit following injection measured by Quest Diagnostics.

3. Study design

In this single-center clinical trial, 20 subjects being treated with testosterone therapy for T deficiency will be randomized to subcutaneous testosterone injection followed by intramuscular testosterone injection or intramuscular testosterone injection followed by subcutaneous testosterone injection. Subjects will be screened for eligibility and subsequently randomized at the baseline visit, then followed for four weeks.

4. Study population

4.1. **Inclusion criteria**

Each patient must meet all of the following inclusion criteria to be enrolled in the study. For laboratory assessment, use the most recent values performed as part of routine clinical care.

- 1) Ability to read, write, and understand English
- 2) Age greater than or equal to 18
- 3) Diagnosed with testosterone deficiency
- 4) Pre-enrollment testosterone concentration of less than 350 ng/dL
- 5) Planning to initiate testosterone treatment at MHB
- 6) Willing to be followed at MHB for at least one month
- 7) Willing to provide informed consent for this study

4.2. **Exclusion criteria**

Patients meeting any of the following exclusion criteria are not to be enrolled in the study. For laboratory assessment, use the most recent values performed as part of routine clinical care.

- 1) Previous exposure to exogenous T, clomiphene citrate, or other Selective Estrogen Receptor Modulators, unless off therapy for at least 12 weeks
- 2) American Urological Association Prostate Symptom score of 15 or greater or significant prostatic symptoms
- 3) History of carcinoma, tumors or induration of the prostate or the male mammary gland, including suspicion thereof
- 4) Pre-enrollment serum PSA more than 4 ng/ml
- 5) Serious psychiatric disease or uncontrolled medical illness, as suspected from the history or clinical examination
- 6) Used any sex hormones or steroidal anabolic drug supplements within 28 days before pre-enrollment testosterone collection or at any time throughout the study
- 7) Incapable of giving informed consent or complying with the protocol

4.3. **Protected populations**

Vulnerable populations will not be enrolled in this study.

5. Modes of Administration

During the study, subjects will be assigned to intramuscular injections, followed by subcutaneous injections or subcutaneous injections, followed by intramuscular injections. Subjects will already have been prescribed testosterone treatment at MHB, participation in the study will only alter the route of administration of T. Subjects will be given standard dosage for bi-weekly T injections (200mg).

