In this randomized, cross-over study 20 subjects who are undergoing testosterone (T) therapy for the treatment of T deficiency will receive both subcutaneous testosterone therapy and intramuscular testosterone therapy. One group will receive a SQ injection followed by an IM injection and one group will receive an IM injection followed by a SQ injection. The primary objective of this study is to measure testosterone concentration in men after these two treatment routes and determine if there are any significant differences due to modes of administration. Endpoints will include total serum testosterone and calculated free testosterone. A questionnaire will also be administered to assess overall patient experience with each route of administration.

Schedule of activities

	Pre-Enrollment (prior to Day 0)	Visit 1 Day 0	Visit 2 Day 3	Visit 3 Day 7	Visit 4 Day 14	Visit 5 Day 17	Visit 6 Day 21	End of Study Day 28
Window	-14 to 0 days	± 0 days	± 2 days	± 2 days	± 2 days	± 2 days	± 2 days	± 2 days
Informed consent	X							
Eligibility assessment ¹ • Laboratory testing ²	SC							
Questionnaires ³	SC	X			X			X
Testosterone Treatment • Pain rating ⁴		SC			SC			
Blood sampling • Beckman Coulter ⁵		X	X	X	X	X	X	X
End of study ⁶								

¹ Eligibility labs: use the most recent values performed as part of routine clinical care: [1] total testosterone, [2] free testosterone, [3] PSA

² Other lab data collected: use the most recent values performed as part of routine clinical care: [1] estradiol, [2] LH, [3] FSH, [4] SHBG, [5] hematocrit

³ Responses collected for: [1] Low Testosterone Questionnaire | © 2014 Men's Health Boston, [2] International Prostate Symptom Score (IPSS) | American Urological Association

⁴ Rating pain after injection on Likert scale

⁵ Samples collected for: visits 1, 4, 7: [1] total testosterone, [2] free testosterone, [3] PSA; visits 2, 3, 5, 6: [1] total testosterone, [2] free testosterone, [3] estradiol, [4] LH, [5] FSH, [6] SHBG, [7] hematocrit, [8] PSA

⁶ End of study survey – preferred mode of administration

X = Research only

SC = Standard care

Table of contents

List of abbreviations and definitions	7
1. Introduction	8
1.1 Background	8
1.2 Rationale and hypothesis.....	8
2. Objectives	8
2.1 Primary outcome and endpoint.....	8
2.2 Secondary outcomes and endpoints.....	8
3. Study design	9
4. Study population	9
4.1 Inclusion criteria	9
4.2 Exclusion criteria.....	9
4.3 Protected populations	9
5. Trial interventions	10

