6.3. Recruitment and consent

A member of the study staff will explain study procedures in detail to the potential subject. The study staff member will clearly outline that the purpose of the study is to compare the testosterone concentrations following two different routes of testosterone therapy. While any study staff member may conduct the informed consent discussion and obtain informed consent, a study physician will be available at all times for any consent-related questions. Undue coercion will be prevented by stressing that participation in this study is voluntary and the future care of the potential subject will not be affected by his decision regarding participation in this study.

7. Activities and measurements

Subjects planning to initiate testosterone treatment via injection at MHB will be consented into the study. Upon enrollment in the study, the randomization will be completed for each subject.

Blood collection will occur before each injection. Subjects will rate pain on the Likert scale following each injection. After treatment with the first mode of T administration (SQ or IM depending on randomization), subjects will come in for blood draws 3 days and 7 days following the injection. Two weeks after the initial injection, subjects will come in for treatment with the second mode of T administration (SQ or IM depending on randomization). Subjects will come in for blood draws 3 days and 7 days following the second injection. Two weeks after the second injection, subjects will complete an end of study assessment with an Investigator and will complete a survey assessing their satisfaction with treatment. Subjects will likely continue testosterone therapy at Men's Health Boston after completion of the study.

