7.4. Subject withdrawals

The Investigator or subjects themselves may stop study treatment at any time for safety or personal reasons.

No replacement of subjects who drop out or are withdrawn following administration of testosterone therapy will take place. Subjects who, having been randomized, do not initiate testosterone therapy may be replaced. The replacement subject will start the study from the beginning.

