8.1. Sample size determination

A total of 20 subjects will enter this study with testosterone deficiency in an age range of 18-70 years. The probability is 80 percent that the study will detect a relationship between the independent and the dependent variables at a two-sided 0.05 significance level, if the true change in the dependent variables is 0.663 standard deviations per one standard deviation change in the independent variable.

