8.2. Analysis of endpoints

Subjects will be summarized by age and other demographic variables. All lab results and responses from low T questionnaires will all be quantitatively analyzed.

9. Risks and benefits of trial participation

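### Section 1.2 hypothesises comparable or acceptable SQ concentrations, but the plan gives no criterion for judging this, and a non-significant difference in 20 men could not support it

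*Combined protocol and SAP*

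**What the plan says.** The hypothesis in section 1.2 reads: "Our hypothesis that SQ will provide comparable or acceptable T concentrations as IM, with regard to duration of action and peak or average concentrations". The sentence before it gives the purpose as to "preliminarily determine if the route of delivery of testosterone therapy affects testosterone concentrations in men".

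The objectives concern differences. The synopsis wants to "determine if there are any significant differences due to modes of administration", and section 2.1 wants to "determine how testosterone concentration in men differs based on administration route for T injections in men". Section 2.1 makes total and calculated free testosterone primary, but selects no time point, peak, average or measure of duration.

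Section 8.1 gives 20 subjects an 80% chance to "detect a relationship between the independent and the dependent variables at a two-sided 0.05 significance level", for an effect of 0.663 SD. The analysis of endpoints in 8.2 comes down to one sentence: "All lab results and responses from low T questionnaires will all be quantitatively analyzed".

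The only testosterone thresholds are below 350 ng/dL for eligibility (4.1) and above 1750 ng/dL on two consecutive draws for stopping an individual (7.5). Neither defines comparable or acceptable.

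Two further provisions bear on the size of the problem. Section 7 schedules the second route with no washout: "Two weeks after the initial injection, subjects will come in for treatment with the second mode of T administration". Section 7.4 says: "No replacement of subjects who drop out or are withdrawn following administration of testosterone therapy will take place".

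**The concern.** A hypothesis of comparability needs a statement of how close is close enough, or at least an interval estimate against which closeness can be judged. The plan supplies neither. Its inferential language is that of a difference test, which suits the objective in 2.1 and the preliminary purpose in 1.2, but not the hypothesis that follows.

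With no rule stated, a p-value above 0.05 is the result most easily taken as support for 1.2. That reading would reward imprecision: the noisier the data and the more men who drop out, the more likely two unlike routes would pass as comparable.

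**Working it through.** **1. The plan's own figure.** Inputs from 8.1: n = 20, effect 0.663 SD, two-sided 0.05. Noncentrality = 0.663 × √20 = 2.965. Power is 0.803 as a paired t test (19 df) and 0.801 as a regression slope with residual SD 1 (18 df). The stated 80% reproduces. The chance of a non-significant result when the difference really is 0.663 SD is therefore 1 − 0.803 = 0.197 or 1 − 0.801 = 0.199, about 20%. No assumed CV is needed.

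**2. The same question as a concentration ratio.** The documents give no within-man CV, so 20% to 50% is assumed. Also assumed: a log-scale two-sequence crossover, equal split, no carry-over in this step, and a true SQ:IM ratio of 0.80.

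- SD of the within-man log difference = √(2 ln(1 + CV²))
- SE = SD × 0.5 × √(1/n₁ + 1/n₂), df = n₁ + n₂ − 2
- P(non-significant) from the noncentral t with noncentrality |ln 0.80| / SE

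Example at CV 30%: SD = √(2 ln 1.09) = 0.415; SE with 10/10 = 0.415 × 0.5 × √0.2 = 0.0928; noncentrality = 0.223 / 0.0928 = 2.40; P(non-significant) = 0.377.

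Because dosed dropouts are not replaced, 16 completers (assumed, 8/8) are also shown.

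| Assumed CV | 20% | 25% | 30% | 40% | 50% |
|---|---|---|---|---|---|
| Non-significant at ratio 0.80, 20 men | 8% | 23% | 38% | 59% | 71% |
| Same, 16 men | 16% | 34% | 48% | 67% | 76% |
| 90% CI: estimate divided and multiplied by, 20 men | 1.11 | 1.14 | 1.17 | 1.24 | 1.30 |
| Same, 16 men | 1.13 | 1.17 | 1.20 | 1.27 | 1.34 |

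The CI factor is exp(t(0.95, df) × SE) at the assumed SD.

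**3. What a comparability rule would deliver.** The rule is that the 90% CI lies wholly inside limits. The documents give no limits; 0.80 to 1.25 is illustrative. Probabilities are by exact integration over the estimated SD.

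| Assumed CV | 20% | 25% | 30% | 40% | 50% |
|---|---|---|---|---|---|
| Power at true ratio 1.0, 20 men | 92% | 73% | 50% | 14% | 3% |
| Same, 16 men | 83% | 57% | 32% | 7% | 1% |
| Completers for 80% power | 16 | 24 | 32 | 54 | 80 |
| False-comparable rate at ratio 0.80, 20 men, no carry-over | 5.0% | 5.0% | 4.9% | 3.0% | 0.9% |
| Same, 10% carry-over | 9% | 8% | 7% | 4% | 1% |

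**4. Carry-over.** Assume that 10% of the period 1 average persists into period 2, with IM = 1 and SQ = 0.80.

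- SQ then IM: the ratio is 0.80 / (1 + 0.1 × 0.80) = 0.80 / 1.08 = 0.741.
- IM then SQ: the ratio is (0.80 + 0.1 × 1) / 1 = 0.90.
- The crossover estimate centres on √(0.741 × 0.90) = 0.816 instead of 0.80.

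This shift applies to any ratio estimate from the design, whether or not a comparability rule is used.

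**The case against.** **No test is prescribed.** The two-sided level appears only in the power sentence of 8.1, and that sentence speaks of a relationship. A reader might infer that the plan commits itself to a difference test and so can never address its hypothesis. The documents do not go that far: 8.2 leaves the method open, and reporting estimates with intervals would comply with it. This stands. The defect is that no analysis or criterion is specified, and that the inferential language which is present points away from the hypothesis.

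**The harm is conditional.** A reader might infer that the investigators intend to treat p>0.05 as proof of comparability. No passage says so. The purpose is preliminary, section 2.1 can be read as estimation, and *acceptable* need not mean equivalent. This also stands, and it is why the default remedy is rewording. But *preliminary* lowers the weight placed on the result without supplying a criterion.

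**The ratio figures rest on assumptions.** The CVs, the 0.80 ratio, the limits, 16 completers and 10% carry-over are all assumed, and 8% to 71% is a wide range. That is fair. The 20% miss rate at 0.663 SD uses only the plan's own figures, and the logical point does not depend on any one CV.

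**The sample size may be adequate.** For a difference of 0.663 SD it is, since 80% reproduces. That power does not carry over to a comparability conclusion.

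**Conclusion.** The concern holds as a mismatch between the hypothesis and the stated inference. Section 1.2 proposes something for which the plan gives no criterion, and a non-significant result would not be evidence for it. The miss rate is about 20% at the plan's own effect. It is 8% to 71% at a true ratio of 0.80 with 20 completers over an assumed CV of 20% to 50%, and 16% to 76% with 16.

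Two stronger readings should be avoided. The first is that 20 men can never support comparability. With limits fixed in advance and a CI inside them they could, but under the illustrative limits power exceeds 80% only near CV 20%. The second is that the 5% false-comparable rate always fails under carry-over. With the assumed 10% carry-over it is exceeded at CV 20% to 30% (9%, 8%, 7%), but not at 40% or 50% (4%, 1%).

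This should be fixed before the data are reviewed. It does not call the sample-size arithmetic or the difference objective into question.

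**What to change.** Default, before data review:

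- **1.2:** restate the hypothesis as an estimation aim, which fits the preliminary purpose. Delete *acceptable* or define it.
- **2.1 and 8.2:** name one exposure summary, for example the time-averaged concentration over each 14-day period, and apply it to both stated primary endpoints, total and calculated free testosterone.
- **8.2:** report the SQ:IM geometric mean ratio with a confidence interval from a crossover model with route, period, sequence and subject. Give the peak (highest sampled value) and day-14 values with intervals as supportive summaries, so that the peak and duration parts of the hypothesis are addressed.
- **8.2:** state that p>0.05 is not evidence of comparability.
- **8.2:** state that the ratio and its interval assume no carry-over, which the 14-day interval without washout does not ensure.

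Only if a comparability conclusion is wanted: justify and fix limits before data review, and conclude comparability only if the 90% CI lies inside them. State power at the expected number of completers, and say that the 5% error rate assumes no carry-over.

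**Cost.** The default changes wording in 1.2, 2.1 and 8.2 and needs no extra patients, visits or samples. Its downside is that it gives no yes/no conclusion on comparability. The optional route needs justified limits and an answer on carry-over. Under the illustrative limits it also needs 16 to 80 completers for 80% power, depending on the CV, so it may call for more than 20 men.

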5.1. Allocation to intervention

Before the study commences, the site will create consecutively numbered envelopes containing randomization schema. Upon a subject enrollment, the next consecutive envelope will be opened to reveal the subject's randomization schema.

6. Subject recruitment and consent

6.1. Subject identification

Potential subjects will be identified by physicians at MHB. Identification will be based on results of standard care labs and review of symptoms in the medical record.

6.2. Screening

A member of the study staff will assess patient eligibility using the Eligibility Checklist. All protected health information used during the screening process of a potential subject will be the minimum necessary for the conduct of this study. Any protected information recorded will be destroyed at the end of the screening process.

For ineligible patients, only the eligibility criteria that were not met (i.e. which criteria excluded the patient from study participation) will be recorded.

6.3. Recruitment and consent

A member of the study staff will explain study procedures in detail to the potential subject. The study staff member will clearly outline that the purpose of the study is to compare the testosterone concentrations following two different routes of testosterone therapy. While any study staff member may conduct the informed consent discussion and obtain informed consent, a study physician will be available at all times for any consent-related questions. Undue coercion will be prevented by stressing that participation in this study is voluntary and the future care of the potential subject will not be affected by his decision regarding participation in this study.

7. Activities and measurements

Subjects planning to initiate testosterone treatment via injection at MHB will be consented into the study. Upon enrollment in the study, the randomization will be completed for each subject.

Blood collection will occur before each injection. Subjects will rate pain on the Likert scale following each injection. After treatment with the first mode of T administration (SQ or IM depending on randomization), subjects will come in for blood draws 3 days and 7 days following the injection. Two weeks after the initial injection, subjects will come in for treatment with the second mode of T administration (SQ or IM depending on randomization). Subjects will come in for blood draws 3 days and 7 days following the second injection. Two weeks after the second injection, subjects will complete an end of study assessment with an Investigator and will complete a survey assessing their satisfaction with treatment. Subjects will likely continue testosterone therapy at Men's Health Boston after completion of the study.

7.1. Data to be recorded

Pre-enrollment

- Low Testosterone Questionnaire
- International Prostate Symptom Score
- Total Testosterone
- Calculated free Testosterone
- Estradiol
- LH
- FSH
- SHBG
- Hematocrit
- PSA

Visits 1 and 4

- Concomitant medication review and adverse event assessment
- Low Testosterone Questionnaire
- International Prostate Symptom Score
- Total Testosterone
- Calculated Free Testosterone
- PSA
- Pain rating following injection

Visits 2, 3, 5, and 6

- Concomitant medication review and adverse event assessment
- Total Testosterone
- Calculated Free Testosterone
- Estradiol
- LH
- FSH
- SHBG
- Hematocrit
- PSA

End of Study

- Concomitant medication review and adverse event assessment
- Low Testosterone Questionnaire
- International Prostate Symptom Score
- Total Testosterone
- Calculated free Testosterone
- PSA
- Survey

7.2. Blood sample collection

At each visit, up to 14mL (approximately 3 teaspoons) of blood will be collected for study purposes. The serum samples (approximately 6mL) will be frozen and shipped to Beckman Coulter for analysis. Whole blood samples (approximately 3mL) will be sent to Quest Diagnostics for analysis.

	At each visit	Total for study
Total amount collected for study	13mL (4 teaspoons)	91mL
Amount of serum shipped to Beckman	6mL	42mL
Amount of whole blood for Quest	4mL	28mL

The Investigator will review all laboratory test results. Laboratory test results that are considered clinically significant by the Investigator will be followed to satisfactory resolution. Laboratory abnormalities are considered to be adverse events only if they result in discontinuation from the study, necessitate therapeutic medical intervention, and/or if the Investigator considers them to be an adverse event.

Beckman Coulter will arrange for samples to be tested for this study. Contact information is listed below:

Name:	[name] Staff Clinical Studies Scientist Beckman Coulter, Inc.
Address:	Immunoassay Business Center [name]
[contact]
Email:	[contact]

Quest will analyze whole blood samples for this study. Contact information is listed below:

Name:	Quest Diagnostics
Address:	[name]
[contact]

Sample collection

Seven blood samples will be obtained throughout the study. Samples will be collected at the following visits:

- Visit 1
- Visit 2
- Visit 3
- Visit 4
- Visit 5
- Visit 6
- End of Study

Sample processing and storage

Whole blood samples from the SST tubes (10mL) will be spun down and resulting serum (6mL) will be transferred to an aliquot tube. Aliquot tubes will be frozen at the site for batch shipping. Whole blood samples from the EDTA tubes (4mL) will remain ambient and will be collected at the site for analysis by Quest Diagnostics. Remaining specimen will be disposed of in biohazard waste receptacle. Beckman Coulter samples will be labeled with a study-specific ID number, date of birth, Visit number, and collection date and time. No other identifiers will be transferred with the samples to the lab. Quest samples will be labeled with a study-specific ID number, date of birth, visit number, and collection date and time. No other identifiers will be transferred with the samples to the lab. The laboratories will not have access to the Master List that links the study-specific ID number with subject identifiers.

Frozen study samples are to be kept at -20°C with an acceptable range of -10° to -30°C. Freezers must maintain constant temperature (i.e. freezers must not be frost-free or defrost automatically). A temperature log will be maintained at the site.

Sample shipping

Frozen samples will be batch shipped at designated times to Beckman Coulter, Inc. Ambient samples will be collected by Quest after each visit.

De-identification of samples

After the master list is destroyed, samples will not be traceable back to individual subjects.

Specimen analysis

Blood sampling will be performed at MHB and analyzed by Beckman Coulter, Inc. and Quest Diagnostics, Inc. Results of the analysis will be provided to MHB and results of the tests may be discussed with subjects, as it pertains to their medical care.

